However, to have power to address the secondary outcomes and because only a portion of the recruited Veterans will have anxiety and depression, we increased the sample size of 134 by 62.7% as described below, resulting in 218 Veterans to be recruited. Although all eligible participants will have diabetes-related distress, we expect depression and anxiety to be prevalent in 25% or more of participating Veterans. Fisher et al. found that 22.5% of those with high diabetes-related distress were clinically depressed. For these secondary outcomes, we initially calculated the sample size based on testing for a large effect size ($d = .80$) between the intervention and usual care groups at a single time point, using a two-group t test with a 0.05 two-sided significance level and power of 80%. Adjusting this to account for correlation among repeated measures results in 18.4 participants per group. Finally, adjustment for 30% attrition at 6 months results in a total needed of 27 per group. Therefore, we need to recruit 218 Veterans, of whom we expect 25% (54) to have anxiety and depression. Thus, we will have 80% power to detect a large effect size of .80 for the secondary outcomes of PHQ-8 and GAD-7. If we based the sample size for the secondary outcomes on detecting a medium effect size of .50, the required sample size of 134 patients would mean increasing the total to 536 patients, a number not feasible for this grant (25% of 536 patients = 134 with anxiety and depression).

In our prior work involving similar recruitment methods, we expect that approximately 7% of those referred to the study from VHA patient databases or community partners will be enrolled in the study (i.e. contact made, interested and eligible for the study). Therefore, we estimate that we will need to attempt to contact approximately 3,114 potential subjects in order to enroll 218 patients in the study.

G2. Data Analysis

Provide a description of your plan for data analysis. State the types of comparisons you plan (e.g. comparison of means, comparison of proportions, regressions, analysis of variance). Which is the PRIMARY comparison/analysis? How will the analyses proposed relate to the primary purposes of your study?

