Outcomes: Primary outcome. We will compare participants in the 2 study arms on baseline characteristics, including sociodemographic characteristics and clinical variables. Based on the Consolidated Standards of Reporting Trials recommendations, we will not provide tests of significance or adjust subsequent analyses for variables found to differ because adjustment may bias the estimated treatment effect. However, because socioeconomic status (SES) and race/ethnicity might impact the mechanism of navigation/coaching, we will include the SES (income and education) and race/ethnicity variables as a priori covariates in our regression analyses. We will examine distributions of the primary outcome (DDS17) and consider transformations, if necessary. We will test for differences between the active intervention and usual care groups using continuous dependent measures (either untransformed or transformed if needed). The random coefficient model will allow us to fit a line for each participant using his/her available data, including participants with missing values, and will maximize the power to detect differences because participants are not removed from the analysis if any time period is missing. Analyses will contain a variable indicating the treatment group, a variable representing the referral source (MEDVAMC and non-MEDVAMC [community social service agencies, or VSOs]), SES and race/ethnicity variables, a variable indicating time (baseline, 3 months, or 6 months), and a term for the interaction of time and treatment. The time-by-treatment interaction is of most interest in this repeated measures analysis because a significant value will indicate a difference between groups over 6 months.

The treatment effect will measure differences between the groups at baseline, and the time effect will measure outcome change over time. By dichotomizing the outcome, we will determine whether the groups differed proportionally in clinically significant improvement on the DDS17. A value of 2.9 or less for the DDS17 will be considered as indicating little or no distress to moderate distress; a value of 3.0 or more will represent high distress. We will test this difference using a logistic regression model in which the dichotomous outcome is the dependent variable. Independent variables will be those for the linear regression models.

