Outcomes: Secondary outcomes. Analyses of the secondary clinical outcomes will be similar to those used for the continuous primary outcomes. We will test assumptions of normality and make transformations as needed. We will then run linear regression models separately for each secondary outcome. The models will include terms for the intervention, time period, time-by-period interaction, the a priori SES and race/ethnicity variables, and the referral source. Significant values for the time-by-treatment interaction will indicate that there were significant differences over time in the secondary outcome. In addition, by dichotomizing the outcomes, we will determine whether the groups differed in having or not having clinically significant changes in PHQ-8 and GAD-7 scores. A 5.0-point decrease in the value of PHQ-8 will be considered a minimally clinically important change⁹⁴ and coded as such; decreases of less than 5.0 points from baseline will be coded as not having achieved clinically significant change. For GAD-7, a score of less than 10 will be considered as having clinical improvement, with scores of 10 or higher representing clinically elevated anxiety symptoms. We will test whether the two groups (clinically significant change vs. no clinical change) differed using a logistic regression model in which the dichotomous outcomes are the dependent variable. The independent variables will be those described above for the linear regression models.

For the secondary outcomes of use of printed/web-based resources, health promotion programs, and clinical care, we will run logistic regression analyses of dichotomized variables (i.e., whether or not the patient used printed/web resources, whether or not he/she used health promotion programs, and whether or not he/she used clinical care during the 6-month follow-up). The models will include terms for the intervention, the a priori SES and race/ethnicity variables, and the referral source. Significant values for the treatment term will indicate that there were significant differences between the iNSPiRED and usual care groups.

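### GAD-7 'clinical improvement' is coded as any score below 10, so participants who start and stay below 10 count as improved

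*Combined protocol and SAP*

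**What the plan says.** Section G2 (Outcomes: Secondary outcomes) adds dichotomised analyses to the continuous models. The stated purpose is to find "whether the groups differed in having or not having clinically significant changes in PHQ-8 and GAD-7 scores".

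The two scales then get different kinds of rule. PHQ-8 is coded on change: a fall of 5.0 points counts, and "decreases of less than 5.0 points from baseline will be coded as not having achieved clinically significant change". GAD-7 is coded on the score reached: "For GAD-7, a score of less than 10 will be considered as having clinical improvement", and 10 or higher is clinically elevated. Both go into one analysis under one pair of labels: "We will test whether the two groups (clinically significant change vs. no clinical change) differed using a logistic regression model".

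On the model, G2 says "The independent variables will be those described above for the linear regression models". Those terms include treatment, time and an interaction, and baseline GAD-7 is not among them. For the primary outcome, whose models the secondary ones resemble, G2 lists "a variable indicating time (baseline, 3 months, or 6 months" as levels of time and adds that "The treatment effect will measure differences between the groups at baseline".

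The inclusion criteria in F1 require a DDS2 mean of 3 or more and set no anxiety threshold. G1 enlarges the sample "because only a portion of the recruited Veterans will have anxiety and depression" and plans on 25% (54 of 218).

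**The concern.** The aim and the category labels speak of change, but the GAD-7 rule measures status. A participant who was never above the threshold meets the rule on entry and keeps meeting it by staying there. A participant with severe symptoms who improves a great deal but stops just above the threshold does not meet it.

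Anxiety symptoms are a named secondary outcome in Section D, so this result may well be reported. On follow-up data, the difference between arms would mix two things: recovery among those elevated at baseline, and staying low among everyone else. The plan would call the whole of it clinically significant change. It would also set that figure beside a PHQ-8 figure that carries the same label and means something different.

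**Working it through.** **1. The plan's own figure.** G1 states no power or sample size for the GAD-7 dichotomy. Its figures for PHQ-8 and GAD-7 concern means, and they reproduce:

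- n per group = 2 × ((1.960 + 0.842)/0.80)² = 24.53
- times the repeated-measures factor [1 + (2 − 1) × 0.5]/2 = 0.75, giving 18.40 (plan: 18.4)
- divided by 0.70 for attrition, giving 26.28, rounded up to 27 per group, 54 in all
- 54/0.25 = 216, and 134 × 1.627 = 218.0 (plan: 218)

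The 25% and the 218 are therefore used below as planned.

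**2. The two rules applied to the same scores.**

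| Baseline → follow-up | GAD-7 rule (below 10) | PHQ-8-type rule (fall of 5 or more) |
|---|---|---|
| 3 → 3 | change | no change |
| 2 → 9 | change | no change |
| 20 → 11 | no change | change (fall of 9) |

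The codes are opposite in all three cases. The PHQ-8 rule also sets no baseline severity, but it does measure change.

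**3. Which rows enter the logistic model.** The text does not settle this.

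- Follow-up rows only: the outcome is status at follow-up, and the label is wrong.
- Baseline rows included: the time-by-treatment interaction does test differential change in being below 10. However, participants are then coded as improved before treatment starts, and every PHQ-8 baseline row is no change by construction.

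**4. Size (illustration).** The documents do not give the share with GAD-7 of 10 or more. The 25% or more in G1 refers to depression and anxiety together, so it serves only as a proxy, and 40% and 50% are shown beside it. Let p be the share elevated at baseline, r the proportion of these who fall below 10 (assumed 35–60%), and s the proportion of the others who stay below 10 (assumed 85–97%).

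- Meeting the rule at baseline = 218 × (1 − p)
- Share of those coded improved who were not elevated at baseline = (1 − p)s / [pr + (1 − p)s]

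| p | Below 10 at baseline | Lowest share (r = .60, s = .85) | Highest share (r = .35, s = .97) |
|---|---|---|---|
| 25% | 163.5 | .6375/.7875 = 81.0% | .7275/.8150 = 89.3% |
| 40% | 130.8 | .510/.750 = 68.0% | .582/.722 = 80.6% |
| 50% | 109 | .425/.725 = 58.6% | .485/.660 = 73.5% |

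**5. The arm comparison.** At one follow-up visit, the risk difference = p·dE + (1 − p)·dN, where dE is the arm difference among those elevated at baseline and dN the difference in staying below 10 among the rest. With assumed dE = 25 points and dN = 6 points:

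- p = 25%: 6.25 + 4.5 points
- p = 40%: 10.0 + 3.6 points
- p = 50%: 12.5 + 3.0 points

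Only the first term in each line is improvement in any ordinary sense.

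**The case against.** The strongest counter-argument starts from G1. The 80% power statement for PHQ-8 and GAD-7 is attached to the roughly 54 participants expected to have anxiety and depression. If the dichotomy were meant for people elevated at baseline, falling below 10 would mean leaving the clinically elevated range, and the label would be broadly apt. But G2 states no such restriction here, although it does define baseline subsets explicitly for new use of VHA and community care. Even with the restriction, 20 to 11 would still be coded as no change. This reading is a further ambiguity to settle; it does not answer the point.

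Second, with baseline rows included, the interaction test is sound. That is correct and is granted above. The individual code is still wrong on that reading, and the plan does not adopt it clearly.

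Third, the size rests on assumptions. This stands. The values of r, s, dE and dN have no source in the documents. Because 25% is stated as a floor, 164 is an upper figure under that proxy. Participants equally stable in both arms cancel out of a risk difference: if dN is zero, the whole difference is recovery among the elevated. The decomposition is on the risk-difference scale at one visit, so it does not translate directly into the planned logistic estimate.

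Fourth, this is a supplementary analysis of a secondary outcome. That is true, and it limits the weight of the point.

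**Conclusion.** The point holds on the text alone: a stated rule gives codes that contradict its stated purpose. It is worth correcting before analysis. It does not threaten the trial's main result. The comparison of arms on GAD-7 below 10 is unbiased by randomisation, and the continuous GAD-7 and primary DDS17 models are unaffected. What the plan cannot support is calling the result clinically significant change.

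Under the proxy and the assumed rates, between half and three quarters of participants already meet the rule at entry, and most of those coded improved would not have been elevated at baseline. Confidence is high for the coding defect and does not extend to those figures. No claim about power is made.

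**What to change.** Define the outcome as GAD-7 below 10 at a named visit, 3 or 6 months. Fit the logistic model to follow-up rows only, with baseline GAD-7 added as a covariate, so that with one visit the treatment term is the test. Do not call the outcome improvement or change. If baseline rows are kept as outcomes instead, leave baseline GAD-7 out of the covariates and name the time-by-treatment interaction as the test.

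If an improvement rate is wanted, report it descriptively among those with baseline GAD-7 of 10 or more, with the numbers shown. Completers per arm are 218 × 0.70/2 = 76.3, so this group is about 19 per arm at 25% prevalence, 31 at 40% and 38 at 50%. For rates near 50%, the 95% half-width for a difference, 1.96 × √(2 × 0.25/n), is about 32, 25 and 22 points. It should therefore not become the main test.

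The DDS17 split at 3.0, which G2 introduces as clinically significant improvement, can be relabelled in the same way. The size of the issue there is unknown, because the share below 3.0 at entry is not given.

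The cost is SAP wording. F2 already collects GAD-7 at baseline, 3 and 6 months, and the main change loses no participants.

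### The PHQ-8 responder model inherits time and time-by-treatment terms although response is zero at baseline by definition, and it names no rows, visit or test term

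*Combined protocol and SAP*

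**What the plan says.** All of this is in Section G2 (Data Analysis), in the paragraphs on the primary and secondary outcomes.

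- **Response.** A PHQ-8 fall of 5.0 points or more counts as a minimally important change; "decreases of less than 5.0 points from baseline will be coded as not having achieved clinically significant change".
- **Model.** "We will test whether the two groups (clinically significant change vs. no clinical change) differed using a logistic regression model". On its terms: "The independent variables will be those described above for the linear regression models".
- **Inherited terms.** For the linear secondary models: "The models will include terms for the intervention, time period, time-by-period interaction", plus socioeconomic status, race/ethnicity and referral source. The interaction as printed is evidently meant to be time by treatment, as the decision rule there shows: "Significant values for the time-by-treatment interaction will indicate that there were significant differences over time in the secondary outcome". The primary-outcome paragraph gives the levels: "a variable indicating time (baseline, 3 months, or 6 months), and a term for the interaction of time and treatment". It adds that "The time-by-treatment interaction is of most interest in this repeated measures analysis" and reads the treatment term as the baseline difference.
- **Contrast.** The logistic models for resource use carry no time terms and do name their test: "Significant values for the treatment term will indicate that there were significant differences between the iNSPiRED and usual care groups".

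The PHQ-8 responder model has no such statement. The sentence on its test describes the two groups by outcome category and names no model term. Section F2 has PHQ-8 collected at baseline, month 3 and month 6.

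**The concern.** Change from baseline is zero at baseline, so any baseline row is a non-response in both arms. A model with a baseline level of time and a time-by-treatment interaction suits a score that varies at baseline. It does not suit this outcome.

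The only reading rules given for the inherited terms are those of the linear models: treatment is the baseline difference, and the interaction is the test. Applied here, they would leave the arm difference in response untested. A null result would then say little about whether more intervention Veterans reached the plan's own important change, and a benefit that fades could yield an interaction pointing against the intervention. As the text stands, the choice of rows and term stays open until data are in hand.

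**Working it through.** **The plan's own figure.** G1 states no power for the responder analysis. Its PHQ-8/GAD-7 sizing does reproduce:
- 2 × (1.960 + 0.842)² / 0.8² = 24.5 per group
- × (1 + 0.5)/2 = 18.4
- / 0.7 = 26.3, rounded up to 27 per group
- 54 / 0.25 = 216, against the stated 218

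**Baseline rows, categorical time.** Both baseline cells are all zero, so both baseline log odds run to minus infinity. The interaction is the follow-up arm difference minus the baseline arm difference, and the latter is undetermined. Take 76 per arm with 15 and 30 responders at each follow-up visit. The model-based standard error of the interaction is 3.6 after 5 Newton iterations, 43.9 after 10, 6,520 after 20 and 79,438 after 25. It depends on where the software stops.

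**Months 3 and 6 only.** The interaction is log OR(month 6) − log OR(month 3). If response is 20% vs 40% at both visits, each log OR is ln(0.4/0.6) − ln(0.2/0.8) = 0.98, and the interaction is 0.98 − 0.98 = 0. That is algebra and holds for any effect constant on this scale. The treatment term in the same model is the arm difference at the reference visit.

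**Baseline rows, linear time.** With the same rates (2,000 simulated trials, 76 per arm, latent correlation 0.5, participant-clustered errors), the median interaction is 0.39 against a true log OR of 0.98. Part of the effect (median 0.70) goes into the treatment term, which the plan reads as a baseline difference. Rejection rates are 14.8% for this interaction, 4.8% for the interaction on months 3 and 6, and 77.8% for the treatment term at month 6.

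**Power from simulated PHQ-8 scores.**
- From the documents: 218 × 0.7 / 2 = 76 per arm; correlation 0.5 (G1).
- Assumed: PHQ-8 mean 8 and SD 5.5, the effect pattern, and that 0.5 also holds between baseline and follow-up (G1 gives it for T = 2 follow-up measurements).
- Method: scores rounded and limited to 0–24, 3,000 replicates, clustered errors, two-sided 0.05, SES, race/ethnicity and referral source omitted. Brackets add baseline PHQ-8.

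| Effect on PHQ-8 | Interaction, baseline rows, linear time | Interaction, months 3 and 6 | Treatment term, months 3 and 6, no interaction | Treatment term, month 6 alone |
|---|---|---|---|---|
| Constant 0.5 SD (response 19% vs 34%) | 10.1% | 5.5% | 68.7% (82.3%) | 51.5% (59.6%) |
| Constant 0.8 SD | 21.9% | 5.2% | 96.9% (99.8%) | 89.7% (95.4%) |
| Growing, 0.25 to 0.8 SD | 63.2% | 42.2% | 74.4% (86.8%) | 89.1% (94.9%) |
| Fading, 0.8 to 0.4 SD | negative in 63% of trials | significant against the intervention in 24.5%, for it in 0.1% | 82.9% (93.5%) | 35.3% (42.1%) |

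Over means 6.3–10 and correlations 0.3–0.7, at a constant 0.5 SD, the four columns run 8.3–11.8%, 4.6–6.0%, 46–89% and 34–75% (unadjusted).

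**Reference-visit treatment term on months 3 and 6, interaction kept.** Two separate runs at 0.5 SD gave 53.1% and 50.4%, against 51.4% and 54.7% for month 6 alone in the same runs. The contrast is sound and costs little or nothing.

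**No arm difference.** With clustered errors these tests reject in roughly 4–6% of trials. The fault is the wrong question and lost power, not false positives.

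**The case against.** A reader might infer that the plan has chosen the interaction as its responder test. The documents do not say so. In G2 the interaction rule comes before the dichotomised analysis and concerns the linear models, while the stated purpose of the dichotomised analysis is whether the arms differ in achieving important change. What is established is an unsuitable set of terms with no named test. That the interaction rule carries over is an inference. This part of the objection stands.

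A reader might also infer that only a month 6 model is sound. That is not so: on months 3 and 6 the treatment term is a valid arm contrast at the reference visit, and only reading the interaction as the test fails.

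It can be said, too, that an analyst would drop the baseline rows, since they hold no change to classify. Probably so, but the inherited time variable has a baseline level and the text makes no exception.

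Finally, 76 per arm uses all randomised Veterans after attrition. G1 sizes PHQ-8 and GAD-7 on about 54 Veterans with anxiety and depression, 27 per group before attrition and about 19 after (27 × 0.7 = 18.9). Whether the responder analysis is limited to them is not stated. With 19 per arm, 0.8 SD and an assumed baseline PHQ-8 of 10 or more, month 6 alone has about 55% power rather than 89.7%. So the absolute powers are illustrations; the algebra and the separation do not depend on them.

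**Conclusion.** The point holds in conditional form. The responder model inherits terms that do not fit an outcome fixed at zero at baseline, and it leaves rows, visit and test term unstated. Harm follows if baseline rows are kept, or if the interaction is read as the test. In the first case the interaction is either inestimable (categorical time) or not the arm difference (linear time). In the second, on months 3 and 6, power for a constant effect is about 5%, and a fading benefit can look like harm. The loss is smaller if the effect grows over time. Month 6 alone, or a treatment contrast at a named follow-up visit, avoids the problem.

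The power figures rest on an assumed PHQ-8 mean, SD, effect pattern and baseline-to-follow-up correlation, and on 76 per arm. The scope is one supportive secondary analysis; the primary DDS17 test, the continuous PHQ-8 analysis and the sample size are untouched. The zero-at-baseline argument should not be extended to the DDS17 and GAD-7 cut-offs, which can be met at baseline. It is worth correcting before analysis because the present wording permits both a sound test and an uninformative one.

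**What to change.** For the PHQ-8 responder model, state that:

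1. Only follow-up rows enter: month 6 alone, or months 3 and 6 by GEE or random-intercept logistic regression. Within-person correlation must be allowed for: on stacked months 3 and 6, plain logistic regression gave 8.2% type I error for the treatment term, against 5.3% with clustered errors.
2. The test is the treatment term, or the treatment contrast at a named visit, as G2 already does for resource use.
3. Baseline PHQ-8 is a covariate.

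This takes about two sentences of plan wording and no new data, since PHQ-8 is already collected at all three assessments. The one small downside is that the odds ratio becomes conditional on baseline PHQ-8, so a marginal risk difference should be reported beside it.
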